HBsAg	Surface antigen of the hepatitis B virus
HBV	Hepatitis B virus
hCG	Human chorionic gonadotropin
HCV	Hepatitis C virus
HIV	Human immunodeficiency virus
HUS	Haemolytic-uremic syndrome
i.a.	Intra-arterial
IB	Investigator's Brochure
ICH	International conference on harmonisation
IEC	Independent ethics committee
i.m.	Intramuscular
INR	International normalised ratio
IRB	Institutional review board
ITP	Immune thrombocytopenic purpura
ITT	Intention-to-treat
IU	International unit
i.v.	Intravenous(ly)
λ_z	Elimination rate constant
K	Potassium
kg	Kilogram
LDH	Lactate dehydrogenase
LLN	Lower limit of normal
LMWH	Low molecular weight heparin
m	Month
MD	Multiple dose
MCH	Mean corpuscular haemoglobin
MCV	Mean corpuscular volume
MCHC	Mean corpuscular haemoglobin concentration
MedDRA	Medical Dictionary for Regulatory Activities
Mg	Magnesium
mg	Milligram
min	Minute
mL	Millilitre
μ L	Microlitre
mm	Millimetre
MRT	Mean residence time
MTD	Maximum tolerated dose
Na	Sodium
NA	Not applicable
NOAEL	No observed adverse effect level
NSE	Neuron specific enolase
NT-proBNP	N-terminal pro B-type natriuretic peptide or N-terminal pro brain natriuretic peptide
OLE	Open label extension
PCI	Percutaneous coronary intervention
PD	Pharmacodynamics
PE	Plasma exchange
PK	Pharmacokinetics
PP	Per protocol

PT	Prothrombin time
PTT	Partial thromboplastin time
QC	Quality control
RBC	Red blood cells
RICO	Ristocetin cofactor activity
RIPA	Ristocetin-induced platelet aggregation
SAE	Serious adverse event
SAP	Statistical analysis plan
SAR	Serious adverse (drug) reaction
S β 100	Protein S-100 beta
s.c.	Subcutaneous(ly)
SD	Single dose
SRT	Simple reaction time
SUSAR	Suspected and unexpected serious adverse reactions
t _{1/2}	Terminal phase half-life
t _{max}	Time to reach C _{max}
TnI	Troponin I
TnT	Troponin T
TRALI	Transfusion related acute lung injury
TTP	Thrombotic thrombocytopenic purpura
ULN	Upper limit of normal
ULvWF	Ultra large vWF
VMEM	Visual memory
vWD	von Willebrand disease
vWF	von Willebrand factor
V _z	Volume of distribution
WBC	White blood cells
WFI	Water for injection
WHO	World health organisation
WLL/DR	Word list learning and delayed recall
WLL/SR	Word list learning and selective reminding
WMEM	Working memory

Nanobody[®] is a registered trademark of Ablynx NV.

LIST OF TABLES

Table 1:	Dosage, method of administration and treatment duration.	22
Table 2:	Overview and current status of clinical trials with anti-vWF Nanobody.	33
Table 3:	Extent of exposure for anti-vWF Nanobody.....	34

1. STUDY SYNOPSIS

Study Title

A Phase II, single-blind, randomised, placebo-controlled trial to study the efficacy and safety of anti-von Willebrand factor Nanobody administered as adjunctive treatment to patients with acquired thrombotic thrombocytopenic purpura

Study Number: ALX-0681-2.1/10

Study Phase: II

Study Centre and Patients

This is a multicentre, multinational study in which it is anticipated to include 110 patients with acquired thrombotic thrombocytopenic purpura (TTP) in approximately 53 participating sites in approximately 13 countries in Europe, Middle East, Australia and Northern America.

This population includes symptomatic patients with acute episodes of acquired TTP, requiring treatment with plasma exchange (PE).

Objectives

Primary

- Reduction of time-to-response, defined by the achievement of laboratory blood marker response, confirmed at 48 hours after the initial reporting of this response

Secondary (including longer-term disease sequelae)

- Improvement in number of subjects responding to therapy
- Reduction in PE procedure-related items
- Reduction of time to resolution or improvement of signs and symptoms typical of TTP, including blood markers
- Reduction of number of exacerbations (defined as recurrent thrombocytopenia following a response and requiring a re-initiation of daily PE treatment after ≥ 1 day but ≤ 30 days after the last daily PE) and relapses (defined as *de novo* event of TTP that occurs later than 30 days after the last daily PE)^{1,2}
- Improvement of cognitive level at steady state post acute phase
- Improvement of clinical symptoms and organ function
- Reduction in mortality within the PE treatment period and within the subsequent study

drug treatment period (including tapering)

- Reduction of concomitant treatment-related complications
- Evaluation of safety and immunogenicity of adjunctive treatment with ALX-0081
- Determination of pharmacokinetic (PK) and pharmacodynamic (PD) characteristics of ALX-0081 in patients with acquired TTP

Endpoints

Primary Endpoint

- Time-to-response, based on the following criteria:
 - Recovery of platelets $\geq 150,000/\mu\text{L}$
 - This response must be confirmed at 48 hours after the initial reporting of platelet recovery equal to or above $150,000/\mu\text{L}$ by a *de novo* measure of platelets $\geq 150,000/\mu\text{L}$ and lactate dehydrogenase (LDH) $\leq 2 \times$ upper limit of normal (ULN) (i.e. “confirmed platelet response”)

Secondary Endpoints

All endpoints achieved within 30 day period after end of study drug treatment:

- Number of subjects with complete remission (defined as confirmed platelet response and absence of exacerbation)^{1,2}
- Number of (subjects with) exacerbations of TTP (defined as recurrent thrombocytopenia following a confirmed platelet response and requiring a re-initiation of daily PE treatment after ≥ 1 day but ≤ 30 days after the last daily PE), and time to first exacerbation of TTP
- Number of subjects relapsing of TTP (defined as *de novo* event of TTP that occurs later than 30 days after the last daily PE)
- Number of daily PE sessions, number of plasma units administered and number of days of daily PE
- Resolution of non-focal neurological symptoms as defined by neurocognitive function at complete remission, measured by a neurocognitive test battery
- Resolution or improvement (improvement of ≥ 1 grade in the Common Terminology Criteria for Adverse Events (CTCAE) v4.0 scale) of TTP-related signs and symptoms as captured on physical examination and as adverse events, at complete remission and at end of the study drug treatment period (including tapering) (by number of

unique subjects and by total number of adverse events (AEs))

- Total mortality within the PE treatment period and within the subsequent study drug treatment period (including tapering)
- Incidence of PE treatment-related AEs, such as, but not restricted to: haemorrhage from catheter insertion, sepsis, catheter thrombosis, pneumothorax, fluid overload, hypoxia, hypotension, anaphylactoid reactions and transfusion related acute lung injury (TRALI)
- Incidence and severity of ALX-0081 treatment-emergent AEs and relationship to study drug
- Development of anti-drug antibodies (ADA) \leq 30 days post-last study drug treatment
- PK and PD profile

Tertiary Endpoints

[REDACTED]

[REDACTED]

[REDACTED]

[REDACTED]

[REDACTED]

[REDACTED]

[REDACTED]

Study Design

This is a Phase II multicentre, single-blinded, parallel design, randomised, placebo-controlled study.

After confirmation of eligibility to study participation, subjects will be randomised in a ratio of 1:1 to either receive ALX-0081 or placebo as adjunctive therapy to PE (Figure 1).

[figure not shown]

Figure 1: Treatment flow chart.
First PE on study: see section 4.2

Subjects will receive a first intravenous (i.v.) bolus of 10 mg ALX-0081 or placebo via push injection within 6h, but not later than 15 minutes prior to the initiation of PE on study (which can either be the very first PE session, if the subject was randomised prior to the initiation of PE, or the second PE session, if the subject was randomised after one, single PE session; see section 4.2). This first PE on study is followed by subcutaneous (s.c.) administration of 10 mg study drug.

Subsequently daily s.c. administrations of 10 mg ALX-0081 (Table 1) or placebo will follow each PE session for the duration of PE (including tapering and PE given for exacerbations) and once daily for 30 days following the very last PE (including tapering) (Table 1). The maximum total daily dose of study drug is 10 mg when administered in conjunction with PE (20 mg only in case twice daily PE sessions are needed) and 10 mg when in the period following the very last PE (including tapering). Study drug administration will continue in case of re-initiation of PE for an exacerbation of TTP, with a maximum total treatment duration limited to 90 days after first administration of study drug.

At \leq 30 days after the last day of study drug administration, subjects will be assessed for the primary and secondary endpoints of the study, and will be followed for a maximum of 1 year for relapses and other tertiary [REDACTED] endpoints.

Laboratory parameters for inclusion, study conduct, safety assessments and assessments of response/relapse, re-treatment and study medication dose modification will be assessed at each local site laboratory.

An independent Data Safety Monitoring Board (DSMB) will monitor accruing safety data during the study (SAEs on an ongoing basis and 'early safety look' when 16 subjects, 8 ALX-0081 treated and 8 placebo-treated, have completed treatment with study drug) and will make recommendations on continuation of the study as appropriate. An interim analysis for safety with formal stopping rules is foreseen when 28 of the ALX-0081 treated subjects have been treated, and will make a recommendation on study continuation or discontinuation. No review of efficacy data by the DSMB is foreseen.

Planned Sample Size

It is anticipated to include 110 patients with acquired TTP.

Study Period

- 30 months recruitment period is anticipated.

- 12 months of follow-up after last administration of study drug (until last subject completes the 12-month follow-up visit).

Duration of Treatment and Follow-up

Treatment with study drug will be continuous during the full time interval of PE and for 30 days after the very last PE (including tapering and PE given for exacerbations). Study drug administration will continue in case of re-initiation of PE for an exacerbation of TTP, with a maximum treatment duration limited to 90 days after first administration of study drug. Subjects will be followed for 12 months after last administration of study drug.

Study Medication

ALX-0081, anti-von Willebrand factor (vWF) Nanobody

ALX-0081 is a clear, colourless solution formulated as a solution for injection. It is provided in sterile, preservative-free, non-pyrogenic, single-use 2R glass vials with injection stoppers and light blue aluminum crimped caps. One vial contains 2.4 mL solution for injection. One mL solution for injection contains as active ingredient 5 mg of ALX-0081 (INN: caplacizumab).

Excipients

Water for injection (WFI), potassium chloride (KCl), potassium dihydrogen phosphate (KH_2PO_4), disodium monohydrogen phosphate ($\text{Na}_2\text{HPO}_4 \cdot 2\text{H}_2\text{O}$), sodium chloride (NaCl), Glycine, Polysorbate 80

Placebo

Placebo is provided in 2R glass vials. One vial contains 2.4 mL solution for injection with identical excipients as ALX-0081.

Storage and Stability

ALX-0081 and placebo are delivered and stored deep frozen at -20°C ($\pm 5^\circ\text{C}$) in the original outer package to be protected from light. Stability studies showed that ALX-0081 is stable at -20°C for at least 3 years and can therefore be stored under these conditions at the investigative site. ALX-0081 contains no antimicrobial preservatives. The study drug must not be used after the expiry date indicated on the labels of the outer package.

Dosage, Method of Administration and Duration

Dosage, method of administration and duration of treatment are summarised in Table 1.

Table 1: Dosage, method of administration and treatment duration.

First study drug administration is 10 mg as an i.v. bolus, administered by a push injection, 15 minutes to 6 hours prior to initiation of PE on study.* This first PE on study is followed by subcutaneous (s.c.) administration of 10 mg study drug.

* As discussed in section 4.2, one PE session prior to randomisation is allowed. In such case, the second PE session will be the first PE on study.

S.c. study drug administration during treatment phase with PE	
Frequency of PE	Treatment administration - daily
1 PE/day	Administer 10 mg study drug within 30 min after end of PE
2 PEs/day	
 For subjects receiving anti-vWF Nanobody: administer 10 mg study drug within 30 min after each PE For subjects receiving placebo, maintain a once daily dosing regimen
Tapering (< 1 PE/day)	Daily administration of 10 mg study drug. On days with PE: within 30 min after end of PE; on days without PE at 24 h (\pm 1 h) after previous administration

S.c. study drug administration (in hospital and at home) for **30 days after the very last PE** (including tapering and PE given for exacerbations)*: 10 mg study drug once daily.

* As discussed in section 7.2, in case of exacerbation of TTP, standard treatment (PE) should be re-initiated and daily administration of study drug continued. The "study drug post-PE" period (for 30 days after the very last PE) will recommence once PE is again stopped. Maximum treatment duration with study drug will be limited to 90 days after first administration of study drug.

If clinically relevant bleeding* occurs

 Stop study drug administration and continue PE if clinically indicated and applicable Assess vWF:Ag and Factor VIII (FVIII) levels**. If FVIII < 10%, assess for anti-FVIII antibodies and if presence is confirmed, permanently discontinue study drug. If vWF:Ag and/or FVIII levels are at a clinically significant low level, initiate i.v. Haemate-P 50 U/kg (or equivalent antihemophilic factor/vWF complex) i.v. Haemate-P treatment should be discontinued when bleeding has clearly stopped and when vWF > 50% Restart study medication at 10 mg daily when bleeding has clearly stopped and when vWF > 50% and FVIII levels are within normal range

* Clinically relevant bleeding is defined as moderate to severe (including life-threatening) bleeding requiring urgent medical and/or surgical intervention.

** FVIII chromogene or other measure of FVIII activity

Criteria for Evaluation

Clinical Outcome

- Time-to-response of treatment, defined by a recovery of platelets \geq 150,000/ μ L. This response must be confirmed at 48 hours after the initial reporting of platelet recovery

above 150,000/ μ L by a *de novo* measure of platelets \geq 150,000/ μ L and LDH \leq 2 X ULN

- Number of subjects with complete remission
- Number of (subjects with) exacerbations of TTP and time to first exacerbation of TTP. Number of subjects relapsing of TTP, and time to first relapse of TTP
- Daily PE data, including serious adverse events (SAEs) related to daily PE treatment
- Neurocognitive function, as measured by a neurocognitive test battery. This test will be preceded by the Glasgow Coma Score to measure the state of consciousness of the subject
- Improvement of organ dysfunction and improvement of TTP related signs and symptoms
- Total mortality
- Determination of biomarkers of TTP including but not limited to disintegrin-like and metalloprotease with thrombospondin repeats 13 (ADAMTS13) levels and anti-ADAMTS13 antibody titres (see also PD assessments)

Safety Assessments

- Incidence and severity of ALX-0081 treatment-emergent AEs and relationship to study drug
- Monitoring of safety markers during treatment, including, but not limited to: platelet count and platelet activation, FVIII, activated partial thromboplastin time (aPTT), prothrombin time (PT), fibrinogen, haemoglobin, cardiac markers, liver function, RICO
- Incidence of clinically relevant bleeding
- Bleeding graded according to the modified immune thrombocytopenic purpura (ITP) Bleeding Score
- Vital signs (blood pressure, heart rate and body temperature)
- Cardiovascular monitoring
- Glasgow Coma Score
- Immunogenicity: development of ADA

PK assessment

Predose plasma concentrations against time will be plotted to demonstrate attainment of steady state.

The plasma concentration-time data of ALX-0081 will be analysed using population PK modeling. Typical population values of basic PK parameters will be estimated together with the inter-individual variability. Effects of subject demographics, laboratory parameter values, and other covariates on the pharmacokinetics of ALX-0081 will be explored. The results of

the population PK analyses will be reported separately in an independent Modeling and Simulation report.

PD assessments

- RICO (conducted at central lab)
- vWF, including vWF:Ag and vWF propeptide (conducted at central lab)
- FVIII chromogene (conducted at central lab)

Inclusion Criteria

1. 18 years of age or older
2. Men or women willing to accept an acceptable contraceptive regimen
3. Patients with clinical diagnosis of TTP
4. Necessitating PE (one, single PE session prior to randomisation into the study is allowed)
5. Subject accessible to follow-up
6. Obtained, signed and dated informed consent

Exclusion Criteria

1. Platelet count greater or equal to 100,000/ μ L
2. Severe active infection indicated by sepsis (requirement for pressors with or without positive blood cultures)
3. Clinical evidence of enteric infection with *E. coli* 0157 or related organism
4. Anti-phospholipid syndrome
5. Diagnosis of disseminated intravascular coagulation (DIC)
6. Pregnancy or breast-feeding
7. Haematopoietic stem cell or bone marrow transplantation-associated thrombotic microangiopathy
8. Known congenital TTP
9. Active bleeding or high risk of bleeding
10. Uncontrolled arterial hypertension
11. Known chronic treatment with anticoagulant treatment that can not be stopped safely, including but not limited to:
 - vitamin K antagonists
 - heparin or low molecular weight heparin (LMWH)
 - non-acetyl salicylic acid non-steroidal anti-inflammatory molecules

12. Severe or life threatening clinical condition other than TTP that would impair participation in the trial
13. Subjects with malignancies resulting in a life expectation of less than 3 months
14. Subjects with known or suspected bone marrow carcinosis
15. Subjects who cannot comply with study protocol requirements and procedures.
16. Known hypersensitivity to the active substance or to excipients of the study drug
17. Severe liver impairment, corresponding to grade 3 toxicity defined by the CTCAE scale. For the key liver parameters, this is defined as follows:
 - bilirubin > 3 x ULN (need to differentiate isolated increase in indirect bilirubin due to haemolysis, this is not an exclusion parameter, but disease related)
 - alanine aminotransferase/aspartate aminotransferase (ALT/AST) > 5 x ULN
 - alkaline phosphatase (AP) > 5 x ULN
 - gamma glutamyl transpeptidase (GGT) > 5 x ULN
18. Severe chronic renal impairment, as defined by GFR < 30 mL/min

Statistical Methods

The primary endpoint (i.e. time-to-response of blood markers comprising recovery of platelets $\geq 150,000/\mu\text{L}$) will be formally assessed by means of a survival analysis. Descriptive statistics for efficacy parameters and secondary/tertiary endpoints (including safety, PK and PD analysis) will be presented for all available data, using either the intention-to-treat (ITT) population, the safety population, or the per protocol (PP) population. Additional information on the study populations that will be included is available in Section 10. A Statistical Analysis Plan (SAP) will be prepared before closing the database and will comprise all methods and tests applied for analysis of the data.

Description of Study Days and Schedules of Assessments

See Table 9 for a general overview of study assessments. Assessments at screening, during the treatment phase and during the follow-up phase are listed in Table 10, Table 11 and Table 13 in Section 8.1, respectively.

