5.4.2 Subject Discontinuation or Withdrawal

Subjects are free to withdraw from participation in this study at any time, for any reason, specified or unspecified and without penalty or loss of benefits to which the subject is otherwise entitled.

Subjects may be withdrawn from the study by the Investigator at any time due to an AE or any other reason if it is the opinion of the Investigator that continued participation in the study is no longer in the best interest of the subject. These reasons include, but are not limited to the following:

- Adverse drug reaction or AE or any other reason for which, in the opinion of the Investigator, subject's continued participation in the study is not in the best interest of the subject
- Withdrawal of consent (subject must be withdrawn)
- Subject fails to return to the site and does not respond to the attempts of the investigational site to contact him (lost to follow-up)
- Protocol violation(s), such as non-compliance with study medication or visit schedule or treatment with prohibited concomitant medications
- Pregnancy (treatment with study drug, if during treatment phase, must be discontinued and subject must be withdrawn from the study)

Relapse of TTP on study (defined as *de novo* event of TTP that occurs later than 30 days after the last daily PE) is not considered a reason for study withdrawal. However re-initiation of study drug treatment as an adjunctive treatment to PE in case of TTP relapse is not permitted.

Subjects discontinuing study drug administration should be encouraged to remain in the study and complete the originally scheduled follow-up visits.

For all subjects withdrawing from the trial for whatever reason, all data will be collected, documented and reported. The case report form (CRF) must be completed up to the time of withdrawal and the Premature Termination Form must be completed. Except for subjects who refuse to return to the investigational site, all subjects withdrawn after at least one administration of study drug should undergo a post-study assessment.

In case of withdrawal from the study due to an AE, subjects should be followed by the Investigator until the AE has resolved.

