* As discussed in section 7.2, in case of exacerbation of TTP, standard treatment (PE) should be re-initiated and daily administration of study drug continued. The "study drug post-PE" period (for 30 days after the very last PE) will recommence once PE is again stopped. Maximum treatment duration with study drug will be limited to 90 days after first administration of study drug.

If clinically relevant bleeding* occurs

- Stop study drug administration and continue PE if clinically indicated and applicable
- Assess vWF:Ag and Factor VIII (FVIII) levels**. If FVIII < 10%, assess for anti-FVIII antibodies and if presence is confirmed, permanently discontinue study drug.
- If vWF:Ag and/or FVIII levels are at a clinically significant low level, initiate i.v. Haemate-P 50 U/kg (or equivalent antihemophilic factor/vWF complex)
- i.v. Haemate-P treatment should be discontinued when bleeding has clearly stopped and when vWF > 50%
- Restart study medication at 10 mg daily when bleeding has clearly stopped and when vWF > 50% and FVIII levels are within normal range

* Clinically relevant bleeding is defined as moderate to severe (including life-threatening) bleeding requiring urgent medical and/or surgical intervention.

** FVIII chromogene or other measure of FVIII activity

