8.1.3 Follow-up

The following procedures have to be performed at scheduled follow-up visits counted in days and months after last study drug administration (3 days \pm 1 day, 7 days \pm 1 day, 1 month \pm 3 days, 2 months \pm 7 days, 3 months \pm 15 days, 6 months \pm 15 days, and 12 months \pm 15 days). Unless stated otherwise, a given action is to be performed at all scheduled follow-up visits:

- Concomitant medication taken since the previous visit must be recorded on the Concomitant Medications page of the CRF. Concomitant medications initiated, stopped, up-titrated or down-titrated for an AE will also be recorded on a specific Concomitant Medications page of the CRF. Transfusion of RBC units will be recorded according to Section 8.2.1.1. This will be done for each transfusion. Data will be recorded as concomitant medication
- Clinical assessment will include physical examination and vital signs (blood pressure and heart rate at rest, body temperature)
- AE recording
- The neurocognitive battery will be administered at the day 3 \pm 1 and 1 year follow-up visits only
- Bleeding score according to the modified ITP bleeding score will be performed at the 1 month follow-up visit
- Assessment of clinically relevant bleeding will be performed at the 1 month follow-up visit
- 12-lead ECG at 1 m follow-up (\pm 3 days), 2 m follow-up (\pm 7 days), 3 m follow-up (\pm 15 days), 6 m follow-up (\pm 15 days), and 12 m follow-up (\pm 15 days)
- Urine pregnancy testing at 1 m follow-up (\pm 3 day) and 3 m follow-up (\pm 3 day) visits (local)
- Blood sampling for chemistry will include the following: glucose, AST, ALT, LDH, CRP, creatinine, urea (BUN), uric acid, protein, albumin, haptoglobin, Na, K, Ca, Mg and Cl (local laboratory)
- Blood sampling for haematology will include the following: haemoglobin, haematocrit, MCV, MCH, MCHC, full blood count including RBC, WBC, differential, reticulocytes, optical platelet count and immature platelet fraction (local laboratory). In case optical platelet counts are not available, they can be replaced by measurements based upon impedance. If not available in the local laboratory, immature platelet fraction measurements can be omitted.
- Blood sampling for coagulation variables will include: fibrinogen, aPTT, PT, INR, vWF:Ag and FVIII chromogene (local laboratory) In case FVIII chromogene is not

available in the local laboratory, it can be replaced by an alternative method (e.g. one stage clotting assay)

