## 1.2 Study Design

This is a Phase II multicentre, single-blinded, parallel design, randomised, placebo-controlled study. After confirmation of eligibility to study participation, adult subjects will be randomised in a ratio of 1:1 to either receive ALX-0081 or placebo as adjunctive therapy to PE. Adolescent subjects will not be randomised and will be treated with ALX-0081.

Adult subjects will receive a first intravenous (i.v.) bolus of 10 mg ALX-0081 or placebo via push injection within 6h, but not later than 15 minutes prior to the initiation of PE on study (which can either be the very first PE session, if the subject was randomised prior to the initiation of PE, or the second PE session, if the subject was randomised after one, single PE session). This first PE on study is followed by subcutaneous (s.c.) administration of 10 mg study drug. Adolescent subjects will receive weight-based doses according to the same administration schedule as adults.

Subsequently daily s.c. administrations of 10 mg ALX-0081 or placebo will follow each PE session for the duration of PE (including tapering and PE given for exacerbations) and once daily for 30 days following the last PE. The maximum total daily dose of study drug is 10 mg when administered in conjunction with PE (20 mg only in case twice daily PE sessions are needed) and 10 mg when in period following last PE. Study drug administration will continue in case of re-initiation of PE for an exacerbation of TTP with a maximum total treatment duration limited to 90 days after first administration of study drug. At 30 days after the last day of study drug administration, subjects will be assessed for the primary and secondary endpoints of the study and will be followed for a maximum of 1 year for relapses and other tertiary (longer-term) endpoints.

Laboratory parameters for inclusion, study conduct, safety assessments and assessments of response/relapse, re-treatment and study medication dose modification will be assessed at each local site laboratory.

[figure not shown]

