Complete remission: Complete remission is defined as recovery of platelets (confirmed by platelets  $\geq 150,000/\mu\text{L}$  and LDH  $\leq 2 \times \text{ULN}$  at 48 hrs after initial platelet response) and absence of exacerbation.

Initial platelet recovery: Date of initial platelet recovery is defined as the first occurrence of platelets  $\geq 150,000/\mu\text{L}$  which is **confirmed** 48 hours later by platelets  $\geq 150,000/\mu\text{L}$  and LDH  $\leq 2 \times \text{ULN}$ . For example, if platelets reach  $\geq 150,000/\mu\text{L}$  on Day 5, are not confirmed at Day 7, reach  $\geq 150,000/\mu\text{L}$  again on Day 10 and are confirmed at Day 12, the initial platelet recovery occurs on Day 10. Initial platelet recovery and confirmation dates will be determined using the actual lab results, following standardisation to consistent units.

Time to Response: Time to response will be calculated as the number of days, hours and minutes (represented by number of days with two significant digits after the decimal point) from study drug administration to initial platelet recovery, as defined above. An

---

observation is censored if the observation does not meet the defined time interval of 30 days, due to any cause of loss-to follow-up (including death), or endpoint not being reached.

Subjects that attain confirmed platelet response:

Time-to-Response = [Date and time (hrs, min) of initial platelet recovery] – [Date and time (hrs, min) of first study drug administration]

Exacerbation: Exacerbation of TTP is defined as recurrent thrombocytopenia following a confirmed platelet response and requiring a re-initiation of daily PE treatment  $\geq 1$  day but  $\leq 30$  days after the last daily PE.

Relapse: Defined as de novo event of TTP that occurs later than 30 days after the last daily PE.

First PE: Defined as start of PE.

First on-study PE: Defined as first PE received after randomisation.

In case first on-study PE is not first PE, then first on-study PE should be started within 24 hours (after the end) of the first PE. If not it is considered major protocol deviation.

Overall duration of study treatment exposure (days): Defined as date of last dose of study treatment – date of first dose of study treatment + 1

Duration of study treatment exposure during daily PE (days): Defined as date of last dose of study treatment during the daily PE period – date of first dose of study treatment during the daily PE period + 1

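### Secondary endpoints are windowed from the end of study drug but timed from the last daily PE, so permanent early stoppers lose countable event days; the SAP tabulation text adds a conflicting first-dose time point

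*Protocol*

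**What the plan says.** **Window.** The protocol synopsis, protocol 4.1.2 and the heading of SAP 6.3.2 all use the rule "All endpoints achieved within 30 day period after end of study drug treatment". The design text ties this to dosing: in the protocol synopsis the time point lies "after the last day of study drug administration, subjects will be assessed for the primary and secondary endpoints of the study", and SAP 1.2 has "At 30 days after the last day of study drug administration, subjects will be assessed for the primary and secondary endpoints of the study". Follow-up visits (protocol 8.1.3) are likewise "counted in days and months after last study drug administration". No rule substitutes a planned end date for a subject who stops early.

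**Event clock.** Exacerbation is recurrent thrombocytopenia with daily PE restarted 1 to 30 days after the last daily PE. Relapse, in SAP 3, is "Defined as de novo event of TTP that occurs later than 30 days after the last daily PE".

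**Drug and PE can separate.** Planned treatment runs through PE and for 30 days after the very last PE, up to 90 days in all. After clinically relevant bleeding, drug is stopped while PE may continue; protocol 7.3 adds "If FVIII < 10%, assess for anti-FVIII antibodies and if presence is confirmed, permanently discontinue study drug". Protocol 5.4.2 allows other early stops and says "Subjects discontinuing study drug administration should be encouraged to remain in the study and complete the originally scheduled follow-up visits".

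**A second counting rule.** The analysis sentences of SAP 6.3.2 tabulate complete remission, exacerbation and relapse one month after the first administration of study drug, which is not the window in that section's heading.

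**The concern.** The two clocks line up only in a subject who takes drug until 30 days after the last daily PE. When drug ends sooner, the window moves forward with the last dose while the exacerbation and relapse periods stay where they are. Events in the lost days become non-events, not censored observations: the ITT population keeps every randomised subject, and SAP 6.1.1 uses the whole population as the default denominator. Because complete remission requires absence of exacerbation, an uncounted exacerbation can turn a failure into a remission. PE counts are also cut when daily PE continues beyond day d+30.

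The truncation depends on stopping drug, which is a post-randomisation event that could differ by arm. Protocol 7.3 names clinically relevant bleeding as the main potential risk of the drug's pharmacological action, and investigators know the allocation (protocol 7.5). An arm with more permanent stops would show fewer relapses and exacerbations, and more remissions, by construction.

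**Working it through.** The plan gives no figure of its own on this point. The sample size of 110 rests on the primary endpoint and does not enter.

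**Inputs.** First dose is day 1, d is the day of the last dose, and L is the day of the last daily PE. The window closes on day d+30. Exacerbation days are L+1 to L+30, and relapse days start at L+31.

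**Formulas under the heading's window**
- Relapse days = max(0, (d+30) - (L+30)) = max(0, d-L).
- Exacerbation days = max(0, min(30, 30-(L-d))).

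For every d ≤ L, with L from 1 to 90, relapse days are 0 and exacerbation days are max(0, 30-(L-d)).

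**Formulas under the SAP analysis sentences** (a month taken as 30 days, so counting ends on day 31)
- Relapse days = 0 for every L ≥ 1, since relapse starts on day 32 at the earliest. With a 31-day month, only a subject whose last daily PE was on day 1 would gain a single day.
- Exacerbation days = max(0, min(30, 31-L)), whatever d is.

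| d | L | Exacerbation days, heading | Relapse days, heading | Exacerbation days, SAP text | Relapse days, SAP text |
|---|---|---|---|---|---|
| 36 (completer) | 6 | 30 | 30 | 25 | 0 |
| 16 | 6 | 30 | 10 | 25 | 0 |
| 3 | 6 | 27 | 0 | 25 | 0 |
| 16 | 16 | 30 | 0 | 15 | 0 |
| 3 | 16 | 17 | 0 | 15 | 0 |
| 3 | 40 | 0 | 0 | 0 | 0 |

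A completer with L = 25 has 6 of 30 exacerbation days under the SAP text.

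**Illustration of size under the heading's window.** All inputs are assumptions; none is in the documents. True relapse risk over the completer's 30 relapse days is p = 15% in both arms. The share stopping permanently early is s = 20% on ALX-0081 and 5% on placebo. Early stoppers keep a fraction c = 0 to 0.5 of the relapse window. Observed risk = p(1-s(1-c)).
- ALX-0081: 0.15 × 0.80 = 12.0% (c = 0) to 0.15 × 0.90 = 13.5% (c = 0.5).
- Placebo: 0.15 × 0.95 = 14.25% to 0.15 × 0.975 = 14.6%.
- Spurious difference: 2.25 to 1.1 points, or about 1.2 to 0.6 subjects of 55 per arm.
- For scale, the standard error of a difference at 15% is √(2 × 0.15 × 0.85/55) = 6.8 points.

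**The case against.** **The last-dose window may not be the rule that gets programmed.** The SAP sentences that specify the tables use first dose. Other text points to a period defined from PE: the mortality analysis in SAP 6.3.2 treats the 30 days after PE as the study treatment period, protocol 4.4 starts follow-up after remission or 90 days of treatment, and protocol 5.4.2 speaks of originally scheduled visits. This stands: reading the end of study drug as the actual last dose is a well-supported inference, not the documents' own wording. It does not rescue the plan. The first-dose rule makes relapse uncountable for everyone, and a sponsor who corrects it by going back to the heading meets the early-stopper problem.

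**A reader might infer that these relapses are lost to the trial.** They are not. Protocol 8.2.1 and SAP 4 also count relapse for up to 1 year, with time to first relapse, and the SAP's combined count of exacerbation and/or relapse states no time limit in its own sentence. But the main report presents the secondary endpoints after the 1-month visit, and 12-month data go to an addendum (protocol 12.10).

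**A reader might infer that every bleed moves the window.** It does not. Bleeding leads to an interruption, with restart foreseen under stated conditions. The bleeding rule requires permanent discontinuation only when FVIII is below 10% and antibodies are confirmed. Only a permanent stop matters here.

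**A reader might infer a demonstrated bias in favour of ALX-0081.** The documents give no rate of permanent stopping and no difference between arms, so direction and size are both conditional.

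**Conclusion.** The point holds in a limited form. Under the wording in protocol 4.1.2 and the SAP 6.3.2 heading, a subject who permanently stops drug on or before the last daily PE contributes no countable relapse day and loses L-d exacerbation days, up to all 30, while staying in the ITT denominator. A subject stopping k days after the last daily PE (k below 30) has k relapse days, against 30 for a completer without tapering. These results are pure day arithmetic and rest only on reading the end of study drug as the last administration.

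The SAP analysis sentences contradict the heading and, as written, make secondary relapse uncountable in all subjects. The two rules must be reconciled.

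Whether the early-stopper truncation favours one arm is unknown. The 1 to 2 points come from assumed inputs and are small against a standard error of 6.8 points. The primary endpoint is untouched, secondary p-values are exploratory, and the 1-year relapse outcome remains. This should be corrected, but it does not threaten the trial's main conclusion.

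**What to change.** State one window in identical words in the protocol synopsis and 4.1.2, the SAP 6.3.2 heading, and the SAP 6.3.2 sentences on complete remission, exacerbation and relapse. Changing the heading alone would leave the first-dose time point in force. The window should apply to every ITT subject and not depend on when drug was actually stopped. Two workable forms are:
- **Planned end of study drug plus 30 days**, with the planned end as the protocol defines it, including the 90-day limit. Without tapering or the limit, this closes on L+60 and gives 30 exacerbation and 30 relapse days to stoppers and completers alike. The limit shortens it (L = 75: close on day 120, relapse from day 106, 15 days), and tapering lengthens the relapse part.
- **A fixed number of days after the last daily PE**, for example 60, which gives 30 and 30 days to everyone. The text should say which course is meant when daily PE is restarted for an exacerbation.

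Keep the actual-last-dose window only as an on-treatment summary.

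The cost is wording and one date derivation. PE sessions are recorded for up to 1 year and follow-up runs 12 months. A few early stoppers will need data from a later scheduled visit, such as the 2-month one, included before the main analysis.
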